Secondary Specific Aim #4. We will determine whether participants randomized to the high intensity exercise intervention have greater improvement or less decline in six-minute walk distance, physical activity, patient-perceived walking performance (measured by the WIQ distance and speed scores), and health-related quality of life measured by the SF-36 PF score at 26 week follow-up, compared to PAD participants randomized to the control group. We hypothesize that participants randomized to the high intensity exercise intervention will have greater improvement or less decline in each outcome at 26-week follow-up compared to the attention control group.

Secondary Specific Aim #5. We will determine whether participants randomized to the high intensity exercise intervention have greater improvement or less decline in six-minute walk distance, maximal treadmill walking time, physical activity, patient-perceived walking performance (measured by the WIQ distance score), and health-related quality of life measured by the SF-36 PF score at 52 week follow-up,

PROTOCOL TITLE: Low InTensity Exercise intervention in PAD: The LITE Trial

compared to PAD participants randomized to the control group. We hypothesize that participants randomized to the high intensity exercise intervention will have greater improvement or less decline in each outcome at 52-week follow-up, compared to the control group.

Secondary Specific Aim # 6.

Preliminary evidence suggests that ischemia-reperfusion, such as that experienced during high-intensity exercise in PAD, is associated with reduced muscle mitochondrial oxidative metabolism and increased oxidative stress (7-9). Therefore, in a randomly selected subset of participants, we will determine whether participants randomized to low intensity exercise (N=50) have greater improvement in calf muscle mitochondrial oxidative metabolism and lesser increases in calf muscle oxidative stress at 52-week follow-up, compared to the high-intensity intervention (N=50). We will also determine whether those randomized to low intensity exercise (N=50) and those randomized to high-intensity intervention (N=50), respectively, have greater improvement in calf muscle mitochondrial oxidative metabolism at 52-week follow-up, compared to the control group (N=50).

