- C. **Randomization.** Participants will be randomized to one of three parallel arms using a SAS computer program. Block randomization will be implemented to ensure balance between the three groups. Randomization will be stratified by according to whether the participants are eligible for (and consented to) muscle biopsy.
- D. **Rationale for focus on walking exercise.** Walking exercise is the only form of exercise that consistently improves walking performance in PAD and is the only exercise currently recommended by practice guidelines for PAD (1,2,27,64).

3.2 Criteria.

Inclusion and exclusion criteria. All participants will have PAD. PAD will be defined as follows. First, an ABI ≤ 0.90 at the baseline study visit is a well-accepted standard for the diagnosis of PAD and will be an inclusion criterion (59-62). Second, people with an ABI of >0.90 and ≤ 1.00 who experience a 20% ankle systolic pressure drop after the heel-rise test will also be included. Third, potential participants with an ABI > 0.90 who have vascular lab evidence of PAD* or angiographic evidence of PAD** who have ischemic symptoms during the six-minute walk and/or treadmill exercise stress test will be eligible. In addition to meeting a criterion for PAD, all participants must be symptomatic, defined by one of the following criteria:; a) ischemic leg symptoms (primarily assessed with the San Diego Claudication

PROTOCOL TITLE: Low InTensity Exercise intervention in PAD: The LITE Trial

Questionnaire); b) report ischemic leg symptoms at the end of the six-minute walk; c) report ischemic leg symptoms at the end of the baseline treadmill stress test; d) walking impairment questionnaire results, e) interview with the potential participant about the presence and nature of leg symptoms during walking activity. Exclusion criteria are listed in Table 3.

* If the only criterion by which a participant is eligible to participate is a toe pressure, the toe pressure must be < 70 or the toe brachial index ratio must be < 0.60 if asymptomatic or < 0.70 if symptomatic.

** Angiographic criteria of PAD consist of a stenosis of 70% or greater in a lower extremity artery.

Table 3. Summary of exclusion criteria and justification for each criterion.

List of specific exclusion criteria	Justification for exclusion criteria
1. Above or below knee amputation, critical limb ischemia, wheelchair confinement, or foot ulcer.	1. Inability to fully participate in the intervention.

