S. Calf muscle biopsy measures. Muscle biopsies will be obtained on consecutive participants who provide informed consent for muscle biopsies until the required number of muscle biopsies is completed. Muscle biopsies may be obtained in up to 30 participants who are found to have a normal ABI consistent with the absence of PAD at their baseline visit. Muscle biopsies will be performed by co-investigator [name] MD, a neurologist with > 30 years of experience performing muscle biopsies. [name] completed all muscle biopsies for our pilot study (Section C3f). The biopsy will be performed in the medial head of the gastrocnemius muscle, at the point that is 67% of the distance between the medial malleolus and the medial aspect of the proximal tibia. This site represents greatest calf muscle diameter in >95% of individuals (88). Anesthesia is achieved with subcutaneous lidocaine. Subcutaneous and adipose tissue are dissected until muscle is identified. Approximately 250 mgs of muscle tissue is removed and immediately frozen at -70 degrees Celsius. The fascia is closed with absorbable suture. The wound is closed with subcuticular sutures and steri-strips. Participants return for a wound check one week later. At 52-week follow-up, we will repeat the measurement using identical techniques, at the site adjacent to the baseline incision. In the open biopsy, muscle tissue is directly visualized, ensuring an optimal muscle tissue sample and providing substantial advantages over the blind needle biopsy. If a participant refuses the open biopsy at either baseline or follow up, a Bergstrom needle biopsy will be offered, which involves using a Bergstrom needle to remove muscle. The Bergstrom needle biopsy method requires a small skin incision. Lidocaine is injected into the skin and subcutaneous tissue. A small incision of the diameter of the needle (5 mm) is made through the skin and superficial fascia of the muscle. The Bergstrom needle is a side-cut tool with a sharp end that includes an inner needle that obtains the muscle specimen. After the Bergstrom needle is advanced directly into the muscle, the inner needle is first withdrawn and then reinserted cutting the muscle that has pushed through the side cut of the outer needle. The entire apparatus is then removed and the specimen is examined. If that tissue is of insufficient size the technique can be repeated. The wound is closed with steri-strips. The biopsy will be performed at the same site as the planned open biopsy. This method avoids the long incision and need for sutures, but has the disadvantage of obtaining a smaller quantity of muscle tissue and has the disadvantage that the physician cannot directly see what tissue he/she is obtaining during the biopsy. Multiple passes with the Bergstrom needle will be required to obtain the amount of tissue usually obtained through the open technique. Specimens are shipped to the Univ. of Florida for measuring 3-nitrotyrosine with Western Blot (89) mitochondrial content (mtDNA copy number) measured by RT-PCR (90) and cytochrome c oxidase (COX) and citrate synthase activities using established methods (91-93). Muscle specimens may be sent to the Universities of Florida and University of Kentucky for analyses that include inflammatory biomarkers, markers of oxidative stress, measures of mitochondrial function and quantity, and muscle myofiber typing. Analyses may also be tested for protein measures of mitochondrial function, macrophages, satellite cells, and PCR/gene expression. Other measures related to skeletal muscle quality and function may also be performed.

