Power estimates. For all primary and secondary aims, we anticipate a 15% drop-out rate at 52-week follow-up, based on 12-month follow-up rates in our GOALS and SILC trials (52,55). We will randomize 305 participants. Of these, 120 will be randomized to the low-intensity intervention, 120 will be randomized to the high-intensity exercise intervention, and 65 will be randomized to the control group. We will enroll more participants in each exercise group than the attention control group because we anticipate that the effect size of the low vs. high intensity exercise comparison will be lower than the effect size of the low intensity vs. the control group. For our Primary Specific Aim, we will have 80% power to detect a minimum difference of 0.43 standard deviations (SD) between the low intensity vs. high intensity exercise groups and a difference of 0.52 SD between the low-intensity and the attention control groups, in change of six-minute walk distance at 52-week follow-up, using two-sided two-sample t-tests **with a significance of 0.025 to adjust for the two comparisons.** Low intensity exercise will be considered effective if either comparison (i.e. with high intensity exercise or with the attention control group) is statistically significant. The SD of the change in six-minute walk in our GOALS and SILC trials was approximately 60 meters. Therefore, our sample size allows us to detect a difference in change in six-minute walk of 26 meters and 31 meters, respectively, between the low vs. high intensity groups and between the low intensity and control groups. Prior studies have defined clinically meaningful changes in the six-minute walk as 30 meters (small meaningful change) and 50 meters (large meaningful change) (102,103). Thus, our power should be adequate to detect a clinically meaningful difference. For our Secondary Aim #1, we will have 80% power to detect a difference of 0.39 SD between the high vs. low intensity exercise interventions and a difference of 0.47 SD between the low-intensity intervention vs. control group, respectively, in changes of six-minute walk, physical activity, WIQ scores, and SF-36 scores at 26 –week follow-up using two-sided two-sample t-tests with a significance of 0.05. For our Secondary Aim #2, we will have 80% power to detect a difference of 0.39 SD between the high vs. low intensity exercise interventions and a difference of 0.47 SD between the low-intensity intervention vs. control group, respectively, in changes of maximal treadmill walking time, physical activity, and WIQ and SF-36 scores at 52-week follow-up, using two-sided two-sample t-tests with a significance level of 0.05. In our SILC trial, the observed differences between the intervention and control groups are 0.61 SD, 0.59 SD and 0.61 SD in changes of maximal treadmill walking time, WIQ distance, and SF-36 physical functioning scores, respectively (52). In a study by Gardner et al of supervised exercise in participants with PAD (73), the observed improvement in physical activity

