
PROTOCOL TITLE: Low InTensity Exercise intervention in PAD: The LITE Trial

level as measured by accelerometer in the exercise group was more than 0.86 SD greater than that for the control group. Thus we should have adequate power to detect similar effect sizes. For our Secondary Aim #3, we will compare rates of ActiGraph-measured adherence to the prescribed exercise intervention (five exercise sessions per week for 45 minutes of walking exercise per session) between the low vs. high intensity exercise groups. Adherence will be defined as achieving at least 80% of the prescribed exercise intervention (see section C18). Based on the home-based component of our SILC trial, we expect the adherence rate in the high intensity exercise group will be about 30%. Our sample size provides 80% power to detect a minimum difference of 19% in the proportion of adherence between the low intensity and high intensity groups, based on the two-sided Z test with pooled variance using normal approximation for binomial distribution with a significance level of 0.05. For our Secondary Aims #4 and #5, we will have 80% power to detect a difference of 0.52 SD between the high-intensity intervention vs. control groups, in changes of six-minute walk distance, physical activity, and WIQ and SF-36 scores at 26-week and at 52-week follow-up, and in change of maximal treadmill walking time at 52-week follow-up, using two-sided two-sample t-tests with a **significance level of 0.05**. Therefore, we have adequate power for detecting differences similar to those observed in SILC trial. For our Secondary Aim #6, we will randomly select 50 participants from each of the three study groups. We will have 80% power to detect a difference of 0.61 SD between the low vs. high intensity exercise interventions, between the low-intensity exercise intervention and the control group, and between the high-intensity exercise intervention group vs. control group, respectively, in changes of citrate synthase, COX, and mitochondrial DNA at 52-week follow-up, using two-sided two-sample t-tests with a significance level of 0.05. In a randomized trial, Timmers et al reported observed differences in citrate synthase, COX, and mitochondrial DNA of 3.17 SD, 2.12 SD, and 0.75 SD, respectively, between a treatment and control group (104). Thus we should have adequate power.

11.3 Steps to secure data to maintain confidentiality during storage, use, and transmission.

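### Secondary Aim #6: the 80% power claim against control depends on biopsying 50 of only 65 controls, which the stated allocation and accrual rules do not secure, and the whole-trial models omit the biopsy stratum

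*Combined protocol and SAP*

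**What the plan says.** On the biopsy sample, Section 11.2 says "For our Secondary Aim #6, we will randomly select 50 participants from each of the three study groups". Section 1.2 (Secondary Specific Aim #6) likewise gives N=50 for each of the three arms and describes a randomly selected subset. The power claim is "We will have 80% power to detect a difference of 0.61 SD between the low vs. high intensity exercise interventions". The same figure is extended to low intensity versus control and high intensity versus control, "in changes of citrate synthase, COX, and mitochondrial DNA at 52-week follow-up, using two-sided two-sample t-tests with a significance level of 0.05". Section 11.2 applies a 15% drop-out rate to all primary and secondary aims.

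On allocation, Section 11.2 assigns 120 to low intensity, and "120 will be randomized to the high-intensity exercise intervention, and 65 will be randomized to the control group". No other allocation is stated anywhere.

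On the biopsy stratum, Section 3.1 C says "Randomization will be stratified by according to whether the participants are eligible for (and consented to) muscle biopsy". No ratio within strata is given.

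On accrual, Section 9.2 S says "Muscle biopsies will be obtained on consecutive participants who provide informed consent for muscle biopsies until the required number of muscle biopsies is completed". It does not say whether that number is a total or a number per arm. Section 22.4, on payments, again refers to random selection among those who agree.

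On the whole-trial models, the repeated-measures model in Section 11.1 contains visit, treatment, their interaction and the baseline six-minute walk, with adjustment for potentially imbalanced confounders such as age and sex. The biopsy stratification factor is not listed.

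**The concern.** The exercise arms can supply 50 biopsied participants from 120 each. The control arm has to supply the same number from 65. Nothing in the plan explains how that is achieved. Randomisation stratified on biopsy consent would, at the only stated ratio, send about one biopsy participant in five to control, and consecutive accrual does not correct for that.

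Two things are at stake. First, two of the three Aim #6 power claims are comparisons with control. If the control biopsy group is smaller than 50, a null result against control would be read as better powered than it was. Second, the one arrangement that delivers exactly 50:50:50 while keeping the overall totals is equal allocation inside the biopsy stratum. That would make biopsy consent strongly associated with arm in the full trial, and the whole-trial models, including the primary one, do not adjust for it.

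**Working it through.** **Inputs.** 50 biopsied per arm (1.2, 11.2); 0.61 SD, 80% power, two-sided 0.05, two-sample t-test (11.2); 15% drop-out (11.2); allocation 120:120:65 of 305 (11.2). The share of participants who are eligible for biopsy and consent is not given, so it is varied below as an assumption.

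**Method.** For group sizes n1 and n2 and a difference d in SD units, the noncentrality is d / √(1/n1 + 1/n2) with n1 + n2 − 2 degrees of freedom. Power is the upper tail of the noncentral t beyond the two-sided 5% critical value.

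**1. The plan's own figure.** 50 × 0.85 = 42.5 per arm. Noncentrality = 0.61 / √(2/42.5) = 2.81. Power is 79.4% (80.3% by the normal approximation). The stated 80% is reproduced, and 0.61 SD already allows for drop-out; with 50 completers per arm the detectable difference would be about 0.57 SD.

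**2. What 50 controls requires.** 50/65 = 77% of the control arm. If biopsy participants follow the overall ratio, 50 controls correspond to 50 × 305/65 ≈ 235 biopsied in total, split about 92:92:50.

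**3. If 150 biopsies follow 120:120:65.**
- Each exercise arm: 150 × 120/305 = 59.0. Control: 150 × 65/305 = 32.0.
- After 15% drop-out: about 50, 50 and 27.
- Exercise versus control (50 vs 27): noncentrality 0.61 / √(1/50 + 1/27) = 2.55; power 71%; difference detectable with 80% power 0.68 SD.
- Low versus high (50 vs 50): noncentrality 0.61 / √(2/50) = 3.05; power 86%; detectable difference 0.57 SD.

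**4. If the exercise arms are capped at 50 and every eligible, consenting control is biopsied.** The exercise arm has 42.5 completers and control has 0.85 × 65 × k, where k is the assumed eligible-and-consenting fraction.

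| k (assumed) | Controls biopsied | Controls with 52-week data | Power at 0.61 SD |
|---|---|---|---|
| 40% | 26 | 22.1 | 63% |
| 50% | 32.5 | 27.6 | 69% |
| 60% | 39 | 33.2 | 74% |
| 70% | 45.5 | 38.7 | 77% |
| 77% | 50 | 42.5 | 79% |

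**5. Against the plan's smallest benchmark.** Section 11.2 cites differences of 3.17, 2.12 and 0.75 SD from a randomised trial. At 0.75 SD, 50 vs 27 gives power of about 87%, compared with about 93% for 42.5 vs 42.5.

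**6. If the biopsy stratum is randomised 1:1:1.** 50:50:50 in that stratum plus 70:70:15 in the other sums exactly to 120:120:65. Biopsy consenters are then 50/65 = 77% of controls but 50/120 = 42% of each exercise arm. Suppose consenters and non-consenters differ by D in mean change after the listed covariates. A model without the stratum then shifts each exercise-versus-control contrast by about (0.77 − 0.42) × D = 0.35 D in size. Low versus high is unaffected.

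**The case against.** The strongest reply is that nothing in the plan's arithmetic fails. Both places that give a control biopsy number say 50, the stated power follows from it, and 50 of 65 is numerically possible. A reader might infer that control will hold only about 32 biopsied participants, so that true power is 71% rather than 80%. The documents do not support that as a fact. It needs the overall ratio to apply inside the biopsy stratum, which Section 3.1 C does not say, and accrual to stop at 150 regardless of arm, which Section 9.2 S does not say. If the required number is read per arm and accrual runs on at the overall ratio without a cap, the result is about 92:92:50 with roughly 89% power against control. If the stratum is randomised equally, the stated power stands.

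Nor is 77% shown to be unreachable. Section 9.2 (minimising biopsy risks) bars anticoagulant users from biopsy. Section 14.1 B describes a switch with physician permission and expects few exclusions. Those two passages must be reconciled, and neither gives a prevalence. Finally, power remains good at the plan's own smallest benchmark.

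All of this stands, and it limits the point to a conditional one. It does not remove it. Equal allocation in the stratum is written nowhere; selecting 50 of 65 controls relies on an unstated consent rate; and continuing until control reaches 50 contradicts N=50 in the exercise arms. Consecutive accrual and random selection are also different rules. Each route leaves something unstated or in conflict.

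**Conclusion.** The stated 80% at 0.61 SD is correct for 50 biopsied per arm and should not be called an error. What holds is that, for the two comparisons with control, it depends on biopsying 77% of the control arm, and the written allocation and accrual rules do not secure that. Under one plausible reading (overall ratio in the biopsy stratum, stop at 150), power against control is about 71% and the detectable difference 0.68 SD. With exercise arms capped at 50 and 40% to 70% of controls assumed eligible and consenting, power is 63% to 77%. Low versus high is not at risk. Aim #6 is a mechanistic secondary aim, and at 0.75 SD the 50 vs 27 case keeps about 87% power, so the plan's general statement of adequacy survives that case.

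The omission of the stratification factor from the Section 11.1 models is worth correcting under any reading. It becomes necessary, to avoid confounding of the control comparisons, if the biopsy stratum was randomised 1:1:1. The documents do not show that it was.

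**What to change.** 1. State the allocation ratio used within the biopsy stratum and whether the required number of biopsies is a total or a number per arm. Reconcile Section 1.2 (Aim #6), Section 3.1 C, Section 9.2 S, Section 11.2 and Section 22.4, including consecutive accrual versus random selection.
2. In Section 11.2, make the 0.61 SD / 80% claim against control conditional on 50 biopsied controls. Add the figures that apply if 150 biopsies follow 120:120:65: about 0.68 SD for each exercise arm versus control and about 0.57 SD for low versus high (80% power, two-sided 0.05, 15% drop-out).
3. Add the biopsy stratification factor as a covariate in the whole-trial models of Section 11.1.

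The cost is wording, one covariate, and possibly a less favourable stated figure against control. No extra participants or biopsies are needed.

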12.0 Provisions to Monitor the Data to Ensure the Safety of Subjects

Serious adverse events will be reported to the DSMB within seven days of each serious adverse event. Adverse event data will be reported to the DSMB every six months during the study, and/or as requested by the DSMB. The DSMB will have the ability to stop the study at any time if there are concerns about safety.

13.0 Withdrawal of Subjects*

Subjects may withdraw from the research at any time. If they decide to leave the research, they should contact the investigator, [name].

If they stop being in the research, already collected data may not be removed from the study database. They will be asked whether the investigator can collect data from their routine medical care. If the subject agrees, this data will be handled the same as research data.

14.0 Risks to Subjects*

14.1 Foreseeable risks.

A. **Risks associated with the exercise program.** First, the exercise program might be associated with an increased risk of heart attack, arrhythmia, or death. In addition, patients may develop ischemic chest pains during exercise. If participants develop chest pain while at a study visit, [name] or [name] will be notified immediately. [name] will oversee arrangement of appropriate follow-up (including immediate transport to the emergency room if appropriate). The exercise physiologist is certified in Cardiopulmonary Resuscitation (CPR) and use of an Automatic External Defibrillator (AED). As recommended by clinical practice guidelines (1), all potential participants will undergo a baseline exercise stress test. Those with an abnormal baseline exercise stress test will be excluded from participation and will be asked to follow-up with their physician. These tests on the heart may lead to the need for procedures to improve the blood flow to your heart or hospitalization if the result on the exercise stress test shows a particularly worrisome result. A treadmill exercise stress test may also be associated with an irregular heartbeat or a heart attack. In addition, those randomized to one of the two home-exercise programs will be educated regarding symptoms to watch for during exercise that should be reported immediately to their physician. Safety manuals and protocols will be developed prior to beginning the intervention. [name] direct line, pager, and cellular telephone number will be provided to all participants.

Second, chest pain during exercise may result in additional cardiac work-up that may lead to procedures to improve coronary blood flow. As indicated above, subjects will be screened for active heart problems with a baseline exercise treadmill test prior to enrollment, according to currently recommended standards of screening PAD patients for coronary artery disease prior to their beginning an exercise program (1). These exercise stress tests will be performed as part of our protocol and interpreted by board-certified cardiologist and co-investigator [name].

PROTOCOL TITLE: Low InTensity Exercise intervention in PAD: The LITE Trial

Participants must have a normal 12-lead exercise stress test to be eligible. Abnormal baseline exercise stress tests may also lead to additional cardiac work-up by the participant's physician that may lead to coronary angiography or coronary revascularization.

Third, exercise may be associated with muscle fatigue or soreness. This typically resolves with rest.

Fourth, it is possible that walking may contribute to foot sores when shoes are poorly fitting. Additionally, walking may worsen or slow healing of foot sores or ulcers in PAD.

Fifth, risks associated with baseline and follow-up testing include loss of balance and falling during the walking tests, chair rises, and standing balance testing. However, the research assistant who will collect these data has been trained to prevent falling. The risk of falling is less than 1 in 200. Falling during these tests may be associated with fracture. The risk of a fracture secondary to a fall during the walking tests is less than 1 in 5,000.

B. Risks associated with the muscle biopsy. The muscle biopsy is associated with several potential risks. These include discomfort during the muscle biopsy procedure, scarring from the muscle biopsy skin incision, bleeding, and infection. Potential participants who are asked to hold or reduce their anti-platelet therapy or anti-coagulation therapy during the week leading up to the muscle biopsy procedure may experience a cardiovascular event related to the temporary reduction or discontinuation of the anti-platelet or anti-coagulant therapy.

To minimize risk, all participants undergoing muscle biopsy will receive a written hand-out regarding signs to watch for of wound infection after the muscle biopsy. They will also be verbally instructed in this. The participant will be instructed to call [name] immediately if any signs of infection occur. In addition, permission from the participant's primary care physician will be required before switching participants on anti-coagulant therapy to low-dose aspirin therapy for the seven days prior to the procedure. If the potential participant's primary care physician does not provide permission for switching to low-dose aspirin for patients taking anti-coagulant therapy, the potential participant will not be eligible for the study. However, based on our pilot study, we anticipate that the number of these exclusions will be very small.

C. Six-minute walk test. The six-minute walk test may be associated with the risk of falling or coronary ischemia or dyspnea due to heart failure or lung disease. Rarely, falling during the six-minute walk test may result in a fracture. However, the research assistant who will collect these data has been trained to prevent falling. The risk of a fracture secondary to a fall during the six-minute walk test is less than 1 in 5,000.

D. Risks associated with ABI measurement. The ankle brachial index measurement consists of measuring systolic blood pressure in each extremity using a hand-held Doppler. The ABI is non-invasive, safe and does not have any known lasting side effects. During the ankle brachial index test, participants may experience discomfort from the inflated blood pressure cuff. However, this discomfort resolves immediately when the cuff is released.

PROTOCOL TITLE: Low InTensity Exercise intervention in PAD: The LITE Trial

E. **Risks associated with drawing blood:** The potential risks of drawing blood include a bruise at the site of vein puncture, inflammation of the vein, and infection. Care will be taken to avoid these complications.

F. **Risks associated with questionnaire administration and qualitative interviewing.** Participation includes a risk of loss of confidentiality regarding personal health information. However, all research staff have undergone formal human subjects training. They are trained to protect the privacy of research subject participants. *Each qualitative interview will be digitally recorded to reduce the need for note taking and to facilitate analysis. When participants consent to the study, we will use a staged consent to ask permission to record the qualitative portion of the interviews to better capture qualitative data. If a participant does not give permission for audio-recording, s/he can still participate in the study. In those cases, the designated interviewer will enter as much of the participant's responses as possible.*

G. **Risks associated with exposing the legs to far-red light for approximately 10 minutes.** There are no known risks associated with the light exposure. The light is bright and can be uncomfortable if the participant looks directly into the light. The light will be directed away from the eyes and the participant will be provided with goggles to wear during the light treatment

14.2 *If applicable, indicate which procedures may have risks to the subjects that are currently unforeseeable.*

Either exercise intervention may have risks that are currently not foreseeable.

